5.7. Ethics

The study will be conducted in accordance with the principles of good clinical practice expressed in the Declaration of Helsinki. All patients will provide their informed consent, and the protocol will be approved by the Ethics Committee of the coordinating hospital (Ramón y Cajal) and each participating center. It will be registered at www.clinicaltrials.gov.

5.8. Study limitations

The main limitations are listed below, followed by the planned compensatory mechanisms:

- 1) Insufficient sample size. There is a possibility that the effect intensity of the "ReDS-guided strategy" might be lower than observed in the two previous studies (reference 19, observational, HR 0.18; reference 20, randomized trial, HR 0.09). Therefore, a conservative sample size calculation with an HR of 0.50 was chosen.
- 2) Futility of the intervention. In case the "ReDS-guided strategy" proves to be futile, an interim analysis of efficacy and safety variables is planned at 30% and 60% of the sample size. It is relevant to consider that in the previous clinical trial (reference 20), there were no significant differences in safety events (arterial hypotension, worsening of renal function, or electrolyte disturbances).

5.9. Execution risks and contingency plan

- 1) Unmasking of the single blind: to minimize this risk, the researchers at each center will be individuals separate from the clinical team responsible for patient care, and the randomization process will be conducted telematically via a mobile application.
- 2) Assignment and validation of clinical events: an ad hoc committee will be formed to review all reported efficacy and safety events, blinded to the study group.

5.10. Patient participation

In order to incorporate the perspective of the patient community throughout the design, execution of the study, and its analysis, the executive committee of the clinical trial includes one representative ([name]) from the Spanish Patient Association CARDIOALIANZA, which brings together 48 patient associations with heart diseases from all over Spain and has shown its support for the project through a letter signed by its president.

5.11. Gender perspective

Within the methodology and data analysis, three aspects related to the gender perspective have been included:

- 1) A quota of at least 30% female patients included in the total population.
- 2) Analysis of the main and secondary efficacy and safety variables by sex.
- 3) Nearly 50% of the researchers from the 25 hospitals involved in the study are women, aiming for parity in representation.

5.12. Adverse events and management

5.12.1. Definition of adverse event related to the device

An adverse event related to the device (AED) is an AE that is related to the use of the investigational device. This includes any AE from inadequate or insufficient information in the instructions for use or any malfunction of the investigational device and any event resulting from erroneous use or intentional misuse of the investigational device (see ISO14155 3.1). Adverse events resulting from the necessary medical procedures for the use of the investigational device, even if not directly related to the device (e.g., moving

the patient to place the device before taking a measurement), will be considered AE related to the procedure.

There are three categories for classifying the relationship of the adverse event of the investigational device:

Clearly unrelated: A relationship between the AE and the investigational device and/or the procedure can be ruled out.

Possibly related: A potential relationship between the investigational device and/or the procedure cannot be ruled out.

Clearly related: It is almost certain that the AE is related to the investigational device and/or procedure.

5.12.2. Definition of deficiency device

A device deficiency (DD) is defined as a failure of the medical device concerning its identity, quality, longevity, reliability, safety, or performance, including failures, misuse errors, and inadequate packaging (see ISO14155 3.15).

The DDs of the investigational device should be reported throughout the study. DDs that caused an adverse event will be reported in the respective adverse events form. If the DD did not cause an adverse event, it should be reported in the adverse events form as a "non-medical" event.

5.12.3. Serious adverse event definition

AEs are classified as serious if one or more of the following consequences are met:

- Led to the death of the patient
- Led to a serious deterioration of the health of the subject, which resulted in:
- An illness or injury with potential life risk, or
- A permanent deficiency of a body structure or function, or
- An extended hospitalization of the patient, or
- A medical or surgical intervention to prevent a life-threatening illness or a permanent disability or deficiency of a body structure or function.

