5. METHODOLOGY

5.1. Study design (annex 1)

A randomized, single-blind, controlled, multicenter clinical trial (list of investigators and participating centers in annex 2) promoted by the researcher, which evaluates the efficacy and safety of a decongestion strategy guided by the ReDS system compared to standard clinical practice in patients admitted for decompensated heart failure.

5.2. Study population

Those adult patients meeting all the following criteria will be included:

- 1. Hospitalized due to HF as the main reason, including the presence of symptoms and signs of congestion, regardless of the left ventricular ejection fraction (LVEF).
- 2. NT-proBNP greater than 1000 pg/L or BNP greater than 300 pg/L upon admission.

Patients meeting any of the following conditions will be excluded:

- 1. Height less than 150 cm or greater than 190 cm or body mass index (BMI) less than 22 or greater than 39, conditions where the use of ReDS is not approved.
- 2. Patients requiring inotropes or vasopressors upon admission, with mechanical support, or heart transplant recipients.
- 3. Any malformation or variant affecting the right lung anatomy (e.g., a pacemaker).
- 4. Patients with any heart disease requiring a planned surgical intervention during the clinical trial (coronary disease, valve disease, or other).
- 5. Chronic kidney disease on hemodialysis.
- 6. Life expectancy less than 12 months due to non-cardiological origin.
- 7. Participation in another clinical trial with intervention.

5.3. Variables

- 1. Primary efficacy variable: combined 30-day outcome of all-cause mortality, heart failure (HF) readmission, or HF-related visits requiring diuretic treatment adjustment.
- 2. Secondary efficacy variable: individual components of the main variable, proportional change in natriuretic peptides and CA125 between admission and the first post-discharge outpatient visit, New York Heart Association functional class at the first post-discharge outpatient visit, average length of stay, cost of hospitalization for HF, and unplanned visit.
- 3. Primary safety variable: combined outcome of symptomatic systolic hypotension (<90 mmHg), electrolyte imbalances (potassium below 3 or above 5.5 meq/L), and/or worsening of renal function compared to the baseline visit at the first post-discharge outpatient visit (at least 50% reduction in glomerular filtration rate).

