5.4. Protocol

Patients will be identified and selected upon admission. If they meet the selection criteria and confirm their willingness to participate in the study, they will be randomized in a 1:1 sequence through a mobile application specifically designed for the study by P INVESTIGA, to one of the following interventions within 48 hours of hospital arrival:

1) "ReDS-guided strategy." Each day, the clinician responsible for the patient will have access to the ReDS value and will adjust the treatment according to the study's diuretic protocol (annex 3). The responsible physician can discharge the patient if the clinical stability criteria are met, and the ReDS value is below 35% and/or a reduction of 15% or more from the admission ReDS value has been achieved. If the ReDS criteria are not met, the patient must remain hospitalized for another day until these conditions are met. Clinical stability is defined as the presence of at least 2 of the following 3 conditions: i) discharge weight lower than admission weight, ii) at least a 20% reduction in natriuretic peptide from admission, and iii) a score <2 in the Orthoedema score.

2) "Usual clinical practice strategy." The responsible physician will not have access to the ReDS values and will adjust the treatment according to their clinical judgment and local practices. Discharge can be given if the clinical stability criteria are met.

The ReDS technology has been described in detail previously (7, 8, 20). Briefly, the ReDS system consists of 2 sensors that are placed (sitting or supine) on the front (infraclavicular) and back (below the scapula) of the patient's right hemithorax and in 45 seconds accurately quantifies the proportion of fluid in the lung. The sensors are connected via 1 cable to a touchscreen monitor that easily guides the measurement process and stores this information. The accuracy of this technology has been validated with high-resolution chest computed tomography (8) and invasive hemodynamic measurements with a Swan-Ganz catheter (9). Normal ReDS values range between 20% and 35% (i.e., 20-35% of the lung would be fluid). Above 35% is considered congestive, whereas below 20% the lung would be "dry" or dehydrated.

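### The seriousness list in Protocol 5.12.3 names an extended hospitalisation but not a new one, so a post-discharge readmission meeting no other criterion gets the 2-week reporting deadline, not the 24-hour one

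*Protocol*

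**What the plan says.** Section 5.12.3 sets the rule for seriousness: "AEs are classified as serious if one or more of the following consequences are met". The list that follows has two branches.

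- The first is the patient's death.
- The second is a serious deterioration in health with one of four results. Three of them are a potential risk to life, lasting damage to the body's structure or function, and treatment given to avert either a life-threatening illness or such damage. The remaining one is the hospital criterion, worded as "An extended hospitalization of the patient, or" in the list.

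Section 5.12.4 defines serious device events by reference to the same consequences.

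Section 5.12.6 ties the site's reporting deadline to seriousness. Its calendar gives 24 hours from detection for serious adverse events, serious device events and unanticipated serious device events, and 2 weeks for other adverse events. Under the same section, the CRO passes serious events, serious device events and certain device deficiencies to the competent authorities.

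Sections 5.5.4 and 5.5.5 place outpatient visits at 14 ± 3 and 30 ± 5 days after discharge. Section 5.3 defines the primary efficacy variable as the "combined 30-day outcome of all-cause mortality, heart failure (HF) readmission, or HF-related visits requiring diuretic treatment adjustment".

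**The concern.** Every patient enters as an inpatient, is discharged, and is then followed as an outpatient for about a month. In the outpatient phase the typical hospital event is a new admission. By then the index stay is over and cannot be prolonged. The one hospital criterion therefore fits the inpatient phase and largely misses the outpatient one.

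The intervention continues after discharge: the summary describes early follow-up in heart failure units based on ReDS values. The harms the protocol singles out in 5.3 (symptomatic hypotension, potassium outside its limits, renal worsening) can bring a discharged patient back to hospital. Speed of reporting is at stake, and with it the flow of information to authorities, ethics committees and those charged with continuous safety control (section 7.2) and risk/benefit monitoring (section 7).

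**Working it through.** No calculation reproduces or refutes a stated figure here. The check is to apply the written rules to one event on either side of discharge.

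Take an episode of symptomatic hypotension that seriously worsens the patient's condition and needs some days of hospital care. Suppose it is not fatal, is judged not to carry potential life risk, leaves no permanent deficiency, and needs no intervention to prevent a life-threatening illness or permanent damage.

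| Step | During the index stay | After discharge |
|---|---|---|
| Death (5.12.3) | No | No |
| Potential life risk | No | No |
| Permanent deficiency | No | No |
| Preventive intervention | No | No |
| Extended hospitalisation | Yes, the stay is prolonged | No, there is a new stay and nothing to prolong |
| New hospitalisation | Not on the list | Not on the list |
| Classification | Serious | Not serious |
| Site deadline (5.12.6) | 24 hours | 2 weeks |
| CRO report to authorities as a serious event (5.12.6) | Yes | No |

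The same event with the same care is classified differently only because of when it occurred. The difference in permitted delay is 14 − 1 = 13 days, within an outpatient phase of about 30 days.

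Four other provisions might close the gap:

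1. **Primary endpoint (5.3).** It captures readmission for heart failure only. An admission for hypotension, potassium disturbance or renal injury is not one of its components. No section says how endpoint readmissions relate to serious-event reporting.
2. **Clinical Events Committee (7.5).** It reviews the events related to the objectives, but no time limit is set.
3. **Outpatient visits (5.5.4, 5.5.5).** Clinical events are recorded at both visits. That is scheduled collection, not expedited reporting.
4. **Reference to ISO 14155.** Section 5.12.6 cites the standard for completing the serious-event form. The protocol writes out its own seriousness criteria in 5.12.3, and the content of the standard is not in the documents.

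None of the four puts the post-discharge event in the right-hand column under the 24-hour deadline.

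The calendar in 5.12.6 has a related defect. It names serious device events (SDAE) in its first row with a 2-week deadline, and again in its second row with a 24-hour deadline. Both cannot apply to the same event.

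**The case against.** The strongest reply is that the list works by any one criterion. Potential life risk and preventive intervention are broad, and an investigator may well apply one of them to a readmission for severe hypotension, hyperkalaemia or renal injury. This stands. A reader might infer that every readmission for harm escapes the 24-hour rule, and the text does not support that. Only readmissions meeting no other criterion are affected.

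A second reply is that the criterion does not say which hospitalisation is extended, so a long stay after readmission could count. That reading is possible. It narrows the gap to shorter readmissions but does not close it, and it leaves sites to decide what counts as extended.

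Three further inferences are tempting and should not be drawn:

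- **Extra days under the ReDS discharge rule counted as serious events.** In the ReDS arm only, section 5.4 says that when the ReDS criteria are unmet "the patient must remain hospitalized for another day until these conditions are met". Section 5.12.3, however, classifies adverse events, and its hospital criterion depends on a serious deterioration in health. A day added only because the ReDS threshold is unmet involves neither, so the present wording already excludes it.
- **A biased test of hypothesis 2.3.** That hypothesis, objective 2.3 and the primary safety variable rest on hypotension, electrolytes and renal function. None uses the seriousness classification, and the protocol states no comparison of serious-event counts between arms. The relevant measurements are taken at both outpatient visits whatever the classification, and section 5.9 provides for review of efficacy and safety events blinded to group.
- **A ceiling from the planning rate.** The 15% rate in section 5.6 applied to one arm gives 0.15 × 507 ≈ 76 patients. That composite includes deaths, which are already serious, and outpatient visits, which are not admissions. It leaves out non-heart-failure readmissions altogether. It does not bound the affected events.

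**Conclusion.** The gap is real but limited. As written, a post-discharge readmission for an adverse event that meets no other seriousness criterion is reported within 2 weeks instead of 24 hours and falls outside the CRO's onward reporting of serious events. Section 5.12.4 carries the same gap into device events. The consequence is slower safety oversight and incomplete serious-event listings for the outpatient phase; the efficacy analysis and the safety composite are untouched.

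The number of affected patients cannot be given, because the documents state no readmission rate for causes other than heart failure and no split of the 15% composite. The conclusion assumes that sites apply the list literally. A site that reads a new admission into the criterion would report in time, but sites would then differ in what they report. This should be corrected: it is a fixed rule that gives a worse safety result, not a detail left for a later document.

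**What to change.** In section 5.12.3, add new or repeat hospitalisation beside extended hospitalisation as a seriousness criterion; section 5.12.4 then follows without further change. In the same place, state whether heart failure readmissions counted in the primary endpoint are exempt from expedited serious-event reporting or follow the 24-hour rule. In the 5.12.6 calendar, reconcile the two rows that name serious device events so that each category has one deadline.

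The cost is a few sentences and some additional expedited forms at sites, fewer if endpoint readmissions are exempted. Because the change touches study procedures, section 5.13 would treat it as a substantial amendment needing ethics committee approval, so it is best combined with any other pending amendment. If patients have already been discharged under the present wording, adverse event records that mention a readmission should be checked against the amended list.

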5.12.4. Serious adverse definition of device

An AE that results in any of the characteristic consequences of a serious adverse event will be considered severe (see ISO14155 3.6).

5.12.5. Non expected serious adverse event

These are defined as unanticipated if by their nature, incidence, severity, or outcome, they have not been identified in the current version of the risk analysis report (see ISO14155 3.42). These events should be reported by the sponsor immediately. An analysis will be conducted to determine the cause, and the immediate possibility of recurrence will be evaluated.

5.12.6. Report responsibility

From the investigator to sponsor

The investigator must document all events in the corresponding CRFs available in the system. The timelines for initial case reports and possible revisions must be strictly followed.

All serious adverse events (SAEs) and serious device adverse events (SDAEs) must be reported along with a justification by completing the SAE-CRF as stipulated in ISO 14155:2011.

For device deficiencies, the DD-CRF must be filled out. Reports must be made considering all available information, even if this involves incomplete reporting. The investigator must follow up on the evolution of AEs if the patient remains in the study, or until the event has been resolved, whichever comes first.

The investigator must categorize each event with a single primary diagnosis. The primary diagnosis can describe the event using various recognizable clinical variables, symptoms, or with secondary diagnoses. Note: Observed symptoms and secondary diagnoses must be appropriately documented in the respective CRF.

Multiple events may occur in the same subject. An individual report must be made for each independent medical event based on the primary diagnosis.

Additionally, the action taken/treatment should also be included along with any available supporting documentation.

The investigator must ensure that all relevant information is available. This also includes information to third parties (family, other hospitals, etc.).

If a patient dies during the study, the investigator must document the cause of death, its circumstances, and place of death. All actions taken, which were initiated to obtain additional information, must be documented in writing and sent to P INVESTIGA.

From the investigator to third parties

According to international and national laws, some of the competent authorities (CAs) and ethics committees may require the reporting of SAEs and device deficiencies with potential for SADEs while the study. Investigators must ensure that they comply with their responsibilities towards their competent authorities and ethics committees.

From the CRO

P INVESTIGA will report all Serious Adverse Events (SAEs)/Serious Device Adverse Events (SDAEs) and all Device Deficiencies with the potential for SDAEs to the competent authorities, as required by local regulatory authorities. Furthermore, P INVESTIGA ensures that safety reports are forwarded to research centers and ethics committees as per local requirements. P INVESTIGA will periodically inform investigators of all reported AEs and DDs that could have generated an SDAE.

Report calendar

The deadlines for reporting adverse events by the investigator to P INVESTIGA will depend on the seriousness of the event:

Event	Report to	Schedule
Adverse Event (AE) /	P INVESTIGATES:	2 weeks
Serious Device Adverse	Document in the AE CRD	
Event (SDAE)		

Serious Adverse Event	P INVESTIGATES:	Immediately, no later than
(SAE) / Serious Device	Document in the AE CRD	24 hours post event
Adverse Event (SDAE)		detection
Unanticipated Serious	P INVESTIGATES:	Immediately, no later than
Device Adverse Events	Document in the AE CRD	24 hours post event
(USDAE)		detection
Device Deficiencies	P INVESTIGATES:	14 days
	Document in the DD CRD	
Device Deficiency with	P INVESTIGATES:	24 hours
potential for SDAE	Document in the DD CRD	

Emergency contact

The ReDS devices used in the study are CE-approved at the time the study begins and will be used according to their intended use. Patients will not receive additional invasive procedures, so there is no need to provide an emergency contact. The informed consent form includes a phone number for each research center where the patient can get medical advice during normal working hours.

5.13. Amendment procedure

If changes to the clinical investigation plan (CIP) are necessary during the study, a justification for the change must be prepared, including the reason for the change. The modification of the CIP can be summarized in a separate document as an appendix to the current version of the CIP or result in a new version of the CIP. If the changes impact procedures related to the study or data analysis, they are defined as substantial. New versions of the CIP or substantial amendments must be reviewed and confirmed by the Coordinating Investigator. All investigators must acknowledge receipt of the amendment through the signature of the approval form for the amendment. Before implementing any changes, substantial amendments must be approved by the ethics committee and, if applicable, by the competent authorities. Non-substantial amendments will only be submitted for notification.

The investigator must not implement any deviation from the CIP without the sponsor's approval and without prior review and documented approval from the EC (and competent authorities if necessary). The only exception would be the need to eliminate an immediate risk to patients or if the change involves logistical and administrative aspects of the study.

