1. SUMMARY

Residual congestion in hospitalized heart failure (HF) patients at discharge is one of the main causes of early readmission. The ReDS (Remote Dielectric Sensing) system is a non-invasive, easy-to-use, and rapid technique that accurately measures the proportion of fluid in lung tissue using RADAR technology. A pilot clinical trial (3 centers, 100 patients) led by the Principal Investigator (PI) demonstrated that guiding decongestion using the ReDS system during hospitalization was associated with a significant reduction in the 30-day readmission rate compared to standard clinical practice, without associated safety events.

Our current objective is to confirm the efficacy and safety of a ReDS-guided decongestion strategy in hospitalized congestive HF patients. To achieve this, an independent, randomized, single-blind clinical trial has been designed, enrolling up to 1,014 congestive HF patients in 25 Spanish hospitals. Patients will be randomized to a decongestion strategy, hospital discharge, and early follow-up in HF units based on ReDS system values versus a strategy based on current clinical practice. All patients will be evaluated daily during hospitalization and in two post-discharge visits (at approximately 10 and 30 days) in HF units using the ReDS system. However, information will only be available to clinicians in the intervention group.

The primary efficacy endpoint will be all-cause mortality, HF readmission, or HF-related decompensations at 30 days. The primary safety endpoint will be the rate of symptomatic hypotension, electrolyte imbalances, or worsening renal function at 30 days.

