4. OBJECTIVES

1. Primary:

1.1. To evaluate whether a ReDS-guided decongestion strategy during hospitalization for HF and early outpatient follow-up is superior to standard clinical practice in reducing the combined event rate of all-cause mortality, HF readmission, or HF visits requiring diuretic adjustment at one month.

2. Secondary:

- 2.1. To analyze the efficacy of a ReDS-guided decongestion strategy in specific clinically relevant subgroups (obesity, chronic renal insufficiency, diuretic resistance) and epidemiological subgroups (age and sex).
- 2.2. To correlate ReDS system measurements with plasma natriuretic peptide and CA125 levels at admission, discharge, and outpatient follow-ups.
- 2.3. To determine the safety of a ReDS-guided decongestion strategy compared to standard clinical practice at one-month post-discharge by evaluating renal function deterioration, symptomatic hypotension, and electrolyte imbalances.
- 2.4. To calculate the cost-effectiveness of a ReDS-guided decongestion strategy considering hospital stay duration and reduction of the combined efficacy endpoint.

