- Complete blood tests (renal and liver function, electrolytes, lipid profile, NTproBNP/BNP, CA125, blood count, and coagulation).
- Alternative methods for congestion analysis used by local clinical practice: lung ultrasound, VExUS, impedance, right heart catheterization.
- Measurement with the ReDS system.
- Clinical events.

5.5.5. Final visit at HF Clinic (30 días+/-5 days after hospital discharge):

- Current NYHA functional class.
- Vital signs (blood pressure, heart rate, arterial saturation) and daily physical examination findings (weight, signs of left and right congestion).
- 12-lead ECG.
- Complete blood tests (renal and liver function, electrolytes, lipid profile, NTproBNP/BNP, CA125, blood count, and coagulation).
- Alternative methods for congestion analysis used by local clinical practice: lung ultrasound, VExUS, impedance, right heart catheterization.
- Measurement with the ReDS system.
- Clinical events.

The information will be stored in a restricted-access online database developed by P INVESTIGA. Only designated researchers at each center will have access to this information.

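### Events still open at the final visit have no required follow-up, and a final visit on days 25 to 29 ends scheduled event collection before day 30

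*Protocol*

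**What the plan says.** **Follow-up of adverse events.** Section 5.12.6 states: "The investigator must follow up on the evolution of AEs if the patient remains in the study, or until the event has been resolved, whichever" is the earlier. The sentence makes no exception for events that are serious or unresolved when the patient leaves.

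**Last contact.** Section 5.5.5 is headed "Final visit at HF Clinic (30 días+/-5 days after hospital discharge". Blood pressure, renal function, electrolytes and clinical events are recorded there. Section 5.5 lists no later visit, call or records check.

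**Endpoint horizon.** The Summary states: "The primary safety endpoint will be the rate of symptomatic hypotension, electrolyte imbalances, or worsening renal function at 30 days". It also sets the primary efficacy endpoint at 30 days. The safety objective in section 4 is a comparison "compared to standard clinical practice at one-month post-discharge". Section 5.3 gives the efficacy outcome a 30-day horizon without a time origin. For safety it refers to "worsening of renal function compared to the baseline visit at the first post-discharge outpatient visit", which section 5.5.4 places at 14 +/- 3 days after discharge.

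**The concern.** There are two points, and they have different causes.

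1. **Outcome of events found late.** The final visit measures what is needed to detect every component of the primary safety variable. Under the section 5.12.6 rule, the duty to follow an event first detected there lapses that same day. Nobody is then required to record whether the renal function recovered or the potassium normalised. The trial sets out to show that a diuretic strategy is as safe as usual care, so this is information that its readers will want.

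2. **Days 25 to 29.** A patient seen on one of these days is within window, yet scheduled collection of events stops before the endpoint horizon is reached. Deaths, readmissions and diuretic-adjustment visits up to day 30 may then be missed. A crude 30-day proportion, and an NNT or NNH built on it, would come out wrong by a small amount.

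The protocol itself fixes both matters as investigator procedures. A statistical analysis plan cannot restore data that were never collected.

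**Working it through.** **Inputs from the protocol**
- Final visit 30 +/- 5 days and first outpatient visit 14 +/- 3 days after discharge (sections 5.5.5 and 5.5.4).
- Primary event rate 15%, a 50% reduction to detect, 507 per group, 10% loss (section 5.6).

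**Assumptions added here**
- The final visit is study exit.
- The 30-day clock starts at discharge.
- The hazard is constant over the 30 days.
- Final visits follow one of two patterns: an even spread over days 25 to 35, or, as the extreme, all on day 25.

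**Point 1: reading the rule against the schedule**
- The follow-up duty ends at min(resolution, exit). For an event detected at the exit visit and unresolved, required follow-up is 0 days.
- This is true for an exit on day 25, day 30 or day 35, so it does not depend on the width of the window.
- The event has already been detected and recorded, so its count as an endpoint event does not change. What is missing is its later course.

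**Point 2: the window**
- Range: 30 - 5 = day 25; 30 + 5 = day 35. That is 11 possible days, of which 5 (days 25 to 29) precede day 30: 5/11 = 45%.
- Mean shortfall with even spread: (5 + 4 + 3 + 2 + 1)/11 = 1.36 days; 1.36/30 = 4.5% of the 30 days.
- Extreme: 5/30 = 16.7%.

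**Events unseen**

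Risk by day d is 1 - (1 - p)^(d/30), with p = 0.15 in controls and 0.075 under the intervention. Expected control events by day 30 are 507 x 0.15 = 76.

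| Final visits | Control risk seen | Intervention risk seen | Control events unseen per 507 | Intervention events unseen per 507 |
|---|---|---|---|---|
| All on or after day 30 | 15.0% | 7.5% | 0 | 0 |
| Even, days 25 to 35 | 14.4% | 7.2% | 507 x (0.1500 - 0.1437) = 3.2 | 1.7 |
| All on day 25 | 1 - 0.85^(25/30) = 12.7% | 1 - 0.925^(25/30) = 6.3% | 507 x (0.1500 - 0.1267) = 11.8 | 6.1 |

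With the 456 per group left after 10% loss (507 x 0.9), the control figures become 456 x 0.0063 = 2.9 and 456 x 0.0233 = 10.6.

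**Effect on crude summaries**
- The ratio of risks barely moves: 0.500, then 0.499, then 0.497.
- The risk difference shrinks from 7.5 to 7.2 or 6.4 percentage points.
- The crude NNT therefore goes from 1/0.075 = 13.3 to 1/0.0720 = 13.9, or to 1/0.0638 = 15.7 in the extreme.

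**Effect on power**

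Comparing two proportions with 456 per group (two-sided 5%, an assumption because the protocol does not state sidedness), power is 95% with complete capture, 94% with even spread and 91% in the extreme. The 95% is what the stated inputs give in this calculation. It differs from the 80% stated in section 5.6, which is a separate matter on which this point does not rest.

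**The case against.** **The analysis allows for early exit.** Section 5.6 uses Kaplan-Meier and Cox methods. A patient last seen on day 26 can be censored there, and the 30-day estimate then draws on those still observed. The window is the same in both arms. Unless early attendance is related to prognosis, the comparison is not biased. This stands, and it limits the harm to fewer observed events and to crude proportions.

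**The clock may not start at discharge.** Section 5.3 gives no origin for efficacy. If time ran from randomisation, five or more further days in hospital would close the gap. This stands for efficacy. For safety, section 4 counts from discharge.

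**Section 5.3 ties safety to the first outpatient visit.** On that reading at least the renal component is assessed on days 11 to 17 and is not cut short. This also stands, but it conflicts with the Summary and section 4.

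**Other sources are contemplated.** Section 5.12.6 asks the investigator to ensure that relevant information is available and mentions family and other hospitals. That does not amount to a planned check at day 30, nor does it extend follow-up of an open event.

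**Stronger readings that the documents do not support**
- A reader might infer that the early end of the window causes the lack of follow-up. It does not: the rule has the same effect at day 35.
- A reader might infer that the follow-up rule distorts the 30-day safety rate or the NNH. It does not: the event is counted, and only its resolution is lost.
- A reader might infer that seriousness cannot be judged, because one criterion is "A permanent deficiency of a body structure or function, or". Section 5.12.3 requires only one of several criteria. Section 5.12.6 sets timelines for an initial report and for revisions, the initial one being due within 24 hours of detection for serious events. Permanence alone may be impossible to judge on the day of detection.

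**Conclusion.** Both points hold, and both are about completeness of data.

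The first is the firmer. As written, no one has to record the outcome of a serious event, or of a component of the primary safety variable, first detected at the final visit. It needs no arithmetic, and its only assumption is that the patient leaves the study at that visit. The protocol implies this by calling the visit final but does not define it.

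The second is modest in size. With an even spread of visits, about 3 control events per 507 go unseen. About 12 is an upper bound that needs every visit on day 25, which is not realistic. Power falls by about 1 percentage point with even spread and 4 in the extreme. The consequence is incomplete capture and crude 30-day proportions that are somewhat too low. The documents give no ground for claiming a biased treatment comparison. For efficacy the point depends on a clock that starts at discharge.

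A contradiction remains in the timing of the primary safety variable: the first outpatient visit in section 5.3, against 30 days in the Summary and one month after discharge in section 4.

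**What to change.** 1. **Section 5.12.6.** State that any serious adverse event, and any component of the primary safety variable, ongoing at the final visit is followed until resolved, stabilised or judged permanent, and that the outcome is recorded.
2. **Section 5.5.5.** Either set the window to day 30 to day 35, or keep 30 +/- 5 and add a telephone or hospital-record status check on or after day 30 for patients seen earlier. In both cases count only events up to day 30 in the 30-day endpoints.
3. **Section 5.3.** Reconcile the time point of the primary safety variable with the Summary and section 4, and state the time origin of the 30-day efficacy outcome.

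**Cost.** The first change needs one amended sentence and an outcome field in the case report form. The status check would fall on about 1,014 x 5/11 = 461 patients if visits spread evenly, before deaths and losses. The alternative narrows the clinic window from 11 possible days to 6. Some patient records would close slightly later. The third change is a wording correction.
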